2.3 Patient disposition, demographics and other baseline disease characteristics

Summary statistics will be provided by treatment arm for demographics and baseline characteristics, including age, age group, sex, race, ethnicity, weight, height, body mass index, category of prior HF medication, chagas disease history, prior HF hospitalization, New York Heart Association class, ejection fraction, NT-proBNP, and vital signs (blood pressure and pulse rate). Body mass index will be calculated as weight (Kg)/height² (m²) from the collected height and weight at the Screening Visit. Continuous variables will be summarized using n, mean, standard deviation (SD), median, minimum, and maximum. Categorical variables will be summarized using frequency and percentage. Additionally, summary statistics will be provided by treatment and age group.

The FAS will be the subject population for the above analyses.

2.3.1 Patient disposition

Patient disposition for all randomized patients will be summarized based on FAS. There will be one combined by-treatment summary showing:

- Count and percent of patients who discontinued study treatment;
- Reasons for study treatment discontinuation;
- Count and percent of patients who voluntarily withdraw consent to participate in the study for any reason at any time;
- Reasons for voluntarily withdrawal;
- Count and percent of loss to follow up;

The screen failure reasons will be recorded on the appropriated eCRF and presented in a separate summary.

2.4 Treatments

2.4.1 Study treatment

The overall duration of exposure will be summarized by the treatment arm. The number of patients who do not tolerate the target dosage and will be titrated down to the lower dose level will be summarized and listed by the treatment arm. The FAS and SAF will be used for this analysis.

The overall duration of exposure to study treatment (sacubitril/valsartan or the active control enalapril) will be calculated in days as: (Date of last administration of study treatment) – (Date of first administration of study treatment) + 1 in each visit interval, and then summed within each level of study medication. The calculation logic shall be as follows for each entry (rows) of intervals within visits:

- For the rows, if the Enalapril_ongoing/Sacubitril_ongoing is 1 (Ongoing) and the next visit Start date is available then we impute End date with available Next visit Enalapril/Sacubitril startDate.
- For rows where end date is missing and the next visit is missed and if its ongoing dose we impute with Start date of same record.
- For the row in the Dosage administration data if the end date is missing and if the dose is not ongoing, we will impute it with corresponding Sacubitril/Enalapril Start date.
- For the last row in the Dosage administration data, if the end date is missing and dose is Ongoing then to impute below date only if its after the dosing Start date :
 - Death date (if available),
 - Last known Patient Alive date
 - Max Visit date Information available
 - if any of the above date is not available then to impute the end date with start date of same record.

- If after all these steps, same inconsistency still generates negative dates (end dates before start dates), then this interval should be considered as zero days.

As the follow up time may vary between participants, the treatment adherence will be presented as percentage from total follow up time as well.

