2.7 Protocol adherence

Medication adherence will be presented as the percentage of time on medication during the study follow-up, excluding any temporary or permanent interruptions due to adverse events or patient choice. The percentage of medication use will be described by mean and standard deviation. Additionally, the number of patients who required temporary or permanent discontinuation of the medication due to adverse events, medical decision, personal choice, or other reasons will be reported.

Moreover, this time will be broken down into mean exposure times to dosages 1, 2, and 3 for each group, similarly, to presented on Figure 2 below.

Figure 2. Titration of the treatment drug at each visit.

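### The SAP's exposure rules, as written, count an ongoing dose before a missed visit as one day and count shared visit days twice, so exposure, adherence and time per dose level are misstated

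*SAP*

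**What the plan says.** SAP 2.4.1 computes duration as last dose date minus first dose date plus one day, "in each visit interval, and then summed within each level of study medication". Its bullets then fill in missing end dates. Numbered here in the order they appear:

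- **Rule 1.** The dose is ongoing and the next visit has a start date: "then we impute End date with available Next visit Enalapril/Sacubitril startDate".
- **Rule 2.** The end date is missing, the dose is ongoing and the next visit did not take place ("the next visit is missed and if its ongoing dose we impute with Start date of same record").
- **Rule 3.** The end date is missing and the dose is not ongoing: the start date is used.
- **Rule 4.** "For the last row in the Dosage administration data, if the end date is missing and dose is Ongoing", the date of death, the date last known alive or the latest visit date is used. The row's own start date is the fallback.
- **Clean-up.** If an end date still precedes its start date, "then this interval should be considered as zero days".

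The same section adds that "the treatment adherence will be presented as percentage from total follow up time as well". SAP 2.7 says "Medication adherence will be presented as the percentage of time on medication during the study follow-up" and splits the time by dose levels 1, 2 and 3. It gives no separate calculation.

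On the protocol side, Section 8 says a missed visit should not automatically lead to discontinuation. Section 6.7.2 says packs cover the time to the next scheduled visit. Section 3 (remote procedures) and the notes to Table 8-1 allow delivery of study drug to the participant's home.

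**The concern.** Rule 2 applies only to rows that the site has marked as ongoing. Setting the end date to the start date nevertheless reduces the whole interval to one day, the same value that rule 3 gives to a dose that had stopped on an unknown date. Rule 4 treats an ongoing last row quite differently and carries it forward. A participant with no dosing record after Month 12 can therefore be credited up to the date last known alive, while one who misses Month 18 and returns on drug at Month 24 is credited with one day for the same period. More complete data can give less exposure.

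Rule 1 errs in the other direction. The next row's start date serves as the last day of one interval and the first day of the next, and the plus-one convention counts it both times. The clean-up step removes only negative intervals.

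At stake are the exposure table, the adherence percentages and the mean time at each dose level by arm, from which readers would see how much drug each arm received.

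**Working it through.** The documents state no exposure or adherence figure, so there is none to reproduce. The rules were applied to the visit schedule in protocol Table 8-1.

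**Assumptions.** One month is 30.4375 days. There is one ongoing row per attended visit, with no recorded end date. Drug is taken every day. Dose level 1 starts on Day 1, level 2 at Week 3 and level 3 at Week 6. The last row closes at the final visit. The reference count takes each calendar day once.

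**Visit days** (Day 1 = 1): Week 3 = 22, Week 6 = 43, Month 4 = 123, Month 8 = 245, Month 12 = 366, Month 18 = 549, Month 24 = 731, Month 36 = 1,097.

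**1. Shared days, no visit missed.** Each row gives end − start + 1, with end equal to the next start. Over 36 months there are 11 rows and so 10 internal boundaries, each counted twice.

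| Follow-up | Rows | Shared days | Rules as written | Each day once | Ratio |
|---|---|---|---|---|---|
| 18 months | 8 | 7 | 556 | 549 | 101.3% |
| 24 months | 9 | 8 | 739 | 731 | 101.1% |
| 36 months | 11 | 10 | 1,107 | 1,097 | 100.9% |

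Levels 1 and 2 become 22 days each instead of 21 (1/21 = +4.8%).

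**2. Month 18 missed, Month 24 attended, 36 months.** The Month 12 row is not the last row.

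- Under rule 2 it counts 366 − 366 + 1 = 1 day.
- Distinct days counted: Day 1 to Day 366 = 366, plus Day 731 to Day 1,097 = 367, total 733.
- Shared days still counted twice: Week 3, Week 6, Week 9, Week 12, Month 4, Month 8, Month 12 and Month 30 = 8.
- Total under the rules: 733 + 8 = 741. Adherence: 741/1,097 = 67.5%.
- If dosing continued to Month 24: 1,097 days, 100%.
- If supply ended the day before Month 18: 1,097 − (731 − 549) = 1,097 − 182 = 915 days, 83.4%.
- Net loss: 915 − 741 = 174 days (15.9 points) to 1,097 − 741 = 356 days (32.5 points).

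The 741 contains both errors, in the same participant.

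**3. Month 8 missed, 36 months.** The rules give 863 days (78.7%). The reference is 1,097, or 1,097 − (366 − 245) = 976 (89.0%) if supply ended at Month 8. The net loss is 10.3 to 21.3 points.

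**4. Week 3 missed.** Level 1 counts as 1 day. It would be 22 − 1 = 21 days if supply ended at Week 3, or 43 − 1 = 42 if the participant stayed on it to Week 6.

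**The case against.** **Next visit may mean next attended visit.** Rule 1 would then carry the Month 12 row to Month 24 and nothing would be lost. The reading is possible, but it leaves rule 2 with last rows only, and there it contradicts rule 4 with no stated order. The text needs correcting either way. What stands is that the one-day result is certain only for rows that are not last, and only if a skipped scheduled visit counts as the missed next visit.

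**Full continuation is the most favourable assumption.** This stands. Packs are planned to last to the next scheduled visit, and home delivery may be arranged but is not assured. The loss is therefore a range. Even the lower bound credits 549 − 366 = 183 days from Month 12 to Month 18, where rule 2 credits one.

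**Rule 2 may rarely apply.** It needs a missing end date together with a missed visit. Protocol 6.6.1 bases exposure on recorded dates, and Section 11.2 provides for queries on missing values. The documents give no count of such rows, so a reader who infers a particular fall in mean adherence has no support for it. Nor do they show that missed visits differ by arm, which is what would be needed for a false difference between arms.

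**The double count is small.** This stands for total exposure. It also arises only where rule 1 supplies the end date; a row with its own recorded end before the next start is unaffected.

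**The results are descriptive.** This stands. A reader might infer that efficacy is compromised, but the primary win ratio uses the FAS with a treatment-policy strategy for discontinuation (SAP 2.5.1, 2.12.1). The exclusions listed for the PPS concern eligibility, not duration of exposure (SAP 2.2). The safety window runs from first dose to 30 days after the last (SAP 2.6.3), not over summed intervals.

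**Conclusion.** The concern holds for the rules as written. SAP 2.4.1 understates exposure for an ongoing, non-last row before a missed visit, and overstates it by one day wherever an end date is borrowed from the next row's start.

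For one missed Month 18 visit over 36 months, the net loss is 15.9 to 32.5 percentage points of adherence, depending on whether drug was available after the missed visit. For a full complier the excess is up to 10 days, or 0.9%. These figures rest on the Table 8-1 schedule, daily dosing and one open-ended row per attended visit.

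Both errors can occur in the same participant. They do not cancel, because their sizes differ so much. The size for the trial as a whole cannot be computed from the documents. It would also go too far to say that the analysis program is wrong: the SAP gives these rules in prose, with no code for them. The correction should be made before the exposure and adherence tables are produced, but it does not bear on the primary result.

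**What to change.** Amend SAP 2.4.1 as follows:

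1. Where the end date is imputed from the next row's start, set it to the day before that start and keep the plus-one.
2. For an ongoing, non-last row whose next visit was missed, carry the dose to the day before the next recorded dosing start. Add a sensitivity analysis that ends it the day before the scheduled date of the missed visit, which is the supply limit.
3. State that rule 4, not rule 2, governs the last row.
4. Report the number of bridged intervals by arm.

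The cost is a few lines of SAP text and code, with no new data. The drawback is that bridging may overstate exposure where no drug was delivered after the missed visit; the sensitivity analysis bounds this. In the Month 18 example the two analyses would give 1,097 and 915 days.

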2.4.2 Prior, concomitant and post therapies

Prior and concomitant medications will be coded according to the latest version of WHO Drug Reference List dictionary which employs the ATC. The number and percentage of patients taking prior and concomitant medications will be summarized for each treatment by ATC class and preferred term (PT). The number and the percentage of participants on different HFrEF background medications will be tabulated by treatment at baseline, during the double-blind stage. The FAS and SAF will be used for these analyses.

2.5 Analysis of the primary objective

2.5.1 Primary Endpoint

The primary endpoint is the hierarchically ordered composite endpoint consisting of time to CV death (worst category; earlier time to CV death is unfavorable), time to first Hospitalization due to Heart Failure (second worst category; earlier time to Hospitalization due to HF is unfavorable) and the relative change from baseline to Week 12 in NT-ProBNP (best category; more reduction or less increase are favorable) (Table 1). CV events will be confirmed by an independent Clinical Endpoint Adjudication Committee (CEC).

The effect is measured through the unmatched win ratio. The win ratio is based on pair-wise comparisons between participants receiving sacubitril/valsartan and participants receiving enalapril. A winner in the pair-wise comparison has a delayed time to the occurrence of CV death; if time to the occurrence of CV death is censored, a winner has a delayed time to the occurrence of first HF hospitalization event; if the times to both cardiovascular events are censored, winner has a smaller change (more

reduction or less increase) in NT-proBNP between baseline and Week 12. The FAS will be used for the primary analysis.

2.5.1.1 Primary Estimand

An estimand is a precise description of the treatment effect reflecting the clinical question posed by the trial objective. It summarizes at a population-level, what the outcomes would be in the same patients under each of the treatment conditions being compared. Attributes of an estimand include the population, variable (or endpoint) and treatment of interest. It also specifies how intercurrent events are addressed and provides a population-level summary for the variable.

Clinical question of Interest: To assess whether sacubitril/valsartan is superior to enalapril in participants with HFrEF caused by chronic Chagas' cardiomyopathy in improving a composite hierarchical outcome.

The primary estimand is described by the following attributes:

1. **Target Population:** Adult chronic Chagas' cardiomyopathy patients with NYHA Class II-IV HFrEF (LVEF $\leq 40\%$) with or without covid-19 events.
2. **Variable:** Composite endpoint in hierarchically order
 1. Time to CV death,
 2. Time to first Heart Failure Hospitalization, and
 3. Relative change from baseline to Week 12 in NT-ProBNP.
3. **Treatment condition:** Sacubitril/Valsartan or Enalapril, regardless of the treatment switching or discontinuation and concomitant use of SGLT2 inhibitors
4. **Intercurrent event (handling strategy):**
 - Non-CV death (while alive)
5. **Summary measure:** Win ratio. Win ratio is the probability that a subject on Sacubitril/Valsartan has a better outcome than a subject on Enalapril divided by the probability that a subject on Enalapril has a better outcome than a subject on Sacubitril/Valsartan.

2.5.1.2 Supplementary Estimand for primary endpoint

This supplementary analysis will be conducted similar to primary endpoint above but on the hierarchically ordered composite endpoint consisting of time to all-cause death, time to first Hospitalization due to Heart Failure (second worst category; earlier time to Hospitalization due to HF is unfavorable) and the relative change from baseline to Week 12 in NT-ProBNP (best category; more reduction or less increase are favorable). When there is treatment crossover, only the data on the randomized treatment for that patient will be considered.

Clinical question of Interest: To assess whether sacubitril/valsartan is superior to enalapril in participants with HFrEF caused by chronic Chagas' cardiomyopathy in improving a composite hierarchical outcome.

1. **Target Population:** Adult chronic Chagas' cardiomyopathy patients with NYHA Class II-IV HFrEF (LVEF $\leq 40\%$) with or without covid-19 events.
2. **Variable:** Composite endpoint in hierarchically order
 1. Time to all-cause death,
 2. Time to first Heart Failure Hospitalization, and
 3. Relative change from baseline to Week 12 in NT-ProBNP.
3. **Treatment condition:** Sacubitril/Valsartan or Enalapril, regardless of the treatment discontinuation and concomitant use of SGLT2 inhibitors
4. **Intercurrent event (handling strategy):**
 - Treatment crossover (While on treatment)
5. **Summary measure:** Win-ratio

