### **6.2.3 Rescue medication**

Participants may receive ACEIs, ARBs, or sacubitril/valsartan during the study **ONLY** if the study drug has been discontinued either temporarily or permanently (see [Section 6.2.2](#) for information on the required washout).

The use of rescue medication must be recorded on the Concomitant medications/Significant non-drug therapies/Dose Administration Record eCRF page.

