Clinical Development

PARACHUTE: Prevention And Reduction of Adverse outcomes in Chagasic Heart failUre Trial Evaluation.

Clinical Study Protocol CLCZ696B3302

**A multicenter, prospective, randomized, open-label,
blinded-endpoint, Phase 4 study to evaluate the efficacy
and safety of sacubitril/valsartan compared with enalapril
on morbidity, mortality, and NT-proBNP change in patients
with chronic Chagas' cardiomyopathy**

Statistical Analysis Plan (SAP)

Document type: SAP Documentation

Document status: Version 2.1

Release date: 29-Apr-2025

Number of pages: 42

Property of Novartis
For business use only
May not be used, divulged, published or otherwise disclosed
without the consent of Novartis

Document History – Changes compared to previous final version of SAP

Version	Date	Changes
1.0	05/11/2020	First Version
2.0	09/04/2025	
• Section 2.6.1 and 2.6.2.4 - Recurrent events included as secondary endpoint.• Section 2.6.1 and 2.6.2.3 - Definition of days alive and out of hospital modified to within one year from randomization.• Section 2.8 - NT-ProBNP evaluation at month 8 included as an exploratory endpoint.• Section 2.5.2.1 - Definition of cardiovascular death included.
		
• Section 2.5.3 - Supplementary analysis for the primary outcome added to account for missing NT-ProBNP values and recurrent events.• Section 2.5.3 - Supplementary analysis for the primary outcome added to account for total death.• Section 2.8 - Exploratory analysis of the time-dependent interaction of SGLT2 inhibitors with treatment included.• Section 2.9 - Subgroup analysis comparing randomizations of COVID-19 during the pandemic period (and after)• Sections 2.5.1.1 and 2.5.1.2 - Estimands definitions
2.1	29/04/2025	
• Section 2.2 - Per protocol set definition updated.• Section 2.1.3 - Added imputation logic for partial missing dates• Section 2.4.1 - Calculation of drug adherence• Section 2.5.2 – Clarification of time to event censoring.• Section 2.9 - Subgroup analyses variables updated

Table of contents

	Table of contents	3
	List of abbreviations	5
1	Introduction	6
1.1	Study design.....	6
1.2	Study objectives and endpoints	8
2	Statistical methods.....	9
2.1	Data analysis general information	9
2.1.1	General definitions	10
2.1.2	Randomization	12
2.1.3	Partial information for dates.....	12
2.2	Analysis sets	13

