2.12 Justification for strategy used in Estimand framework

2.12.1 Primary Estimand

Table 5. Justification for strategy used in Estimand framework

Intercurrent Event	Strategy	Clinical Justification
Treatment discontinuation	Treatment policy	Treatment discontinuation is included in the treatment conditions of interest.
Non-CV death	While Alive	Only data before non-CV death is considered. Death naturally ends the observation period, only the observed part before the non-CV death should be taken into consideration.
Concomitant use of SGLT2 Inhibitor	Treatment policy	Concomitant use of SGLT2 inhibitor is included in the treatment conditions of interest. Use of this concomitant medication will be observed in both arms and is a usual clinical practice.
Covid-19	Treatment policy	Covid-19 is included in the target population of interest.
Treatment crossover (Switch after observing endpoint)	Treatment policy	Treatment crossover is included in the treatment condition of interest (since the switch doesn't have the confounding effect on the observed endpoint)
Treatment crossover (Switch before observing endpoint)	Treatment policy	Treatment crossover is included in the treatment condition of interest

before observing endpoint)		
-------------------------------	--	--

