2.12.2 Supplementary Estimand for primary endpoint

Table 6. Justification for strategy used in Estimand framework

Intercurrent event	Strategy	Clinical Justification
Treatment discontinuation	Treatment policy	Treatment discontinuation is included in the treatment conditions of interest.
Non-CV death	Composite strategy	No differentiation between CV and Non-CV death, consider any death as the endpoint. Non-CV death is included in the Estimand endpoint.
Concomitant use of SGLT2 Inhibitor	Treatment policy	Concomitant use of SGLT2 inhibitor is included in the treatment conditions of interest. Use of this concomitant medication will be observed in both arms and is a usual clinical practice.
Covid-19	Treatment policy	Covid-19 is included in the target population of interest.
Treatment crossover	While on treatment	The data is censored at the time of the switch and no imputation is performed for NTProBNP

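### The only all-cause-death win ratio also censors at treatment crossover, so its difference from the primary result cannot be attributed to counting non-CV death

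*SAP*

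**What the plan says.** The primary estimand (SAP 2.5.1.1) has CV death as its first tier and applies a while-alive strategy to non-CV death, so those deaths are censored and not counted. Its treatment condition holds "regardless of the treatment switching or discontinuation and concomitant use of SGLT2 inhibitors". Table 5 (SAP 2.12.1) lists switches before and after the endpoint, both under treatment policy: "Treatment crossover is included in the treatment condition of interest".

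The supplementary estimand (SAP 2.5.1.2) makes all-cause death the first tier. Table 6 (SAP 2.12.2) explains: "No differentiation between CV and Non-CV death, consider any death as the endpoint". For crossover, 2.5.1.2 states: "When there is treatment crossover, only the data on the randomized treatment for that patient will be considered". Table 6 labels this while on treatment and adds: "The data is censored at the time of the switch and no imputation is performed for NTProBNP". Discontinuation stays under treatment policy in both estimands, and both give the same clinical question.

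The SAP document history for version 2.0 records: "Supplementary analysis for the primary outcome added to account for total death". Switching is possible in this trial. Protocol 6.2.3 says "Participants may receive ACEIs, ARBs, or sacubitril/valsartan during the study", on condition that study drug has been stopped temporarily or for good.

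**The concern.** Non-CV death and crossover are separate threats to the primary answer in an open-label trial whose test drug is commercially available. A supplementary analysis that counts non-CV deaths is useful if a reader can set it beside the primary result and see what counting them did. Here the comparison mixes two changes.

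The second change also acts on the tier of interest. If switches tend to follow an HF hospitalisation, when the risk of death is raised, censoring at the switch is informative and removes deaths from an analysis meant to count all of them. If switching is more common in one arm, the two changes can partly cancel, and the primary result then looks more robust to non-CV death than it is.

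**Working it through.** **The two estimands side by side**

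| Attribute | Primary (2.5.1.1, Table 5) | Supplementary (2.5.1.2, Table 6) |
|---|---|---|
| First tier | CV death | All-cause death |
| Non-CV death | While alive (censored) | Composite (counted) |
| Crossover | Treatment policy | While on treatment (censored at switch) |
| Discontinuation, SGLT2 inhibitor, COVID-19 | Treatment policy | Treatment policy |

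The other supplementary win ratios, in SAP 2.5.3, cover the per-protocol set and total HF hospitalisations. Neither uses all-cause death.

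Let A be the primary win ratio, B the all-cause-death win ratio with switches ignored, and D the all-cause-death win ratio censored at the switch. Then D − A = (B − A) + (D − B). The first term is the effect of counting non-CV death, the second the effect of censoring. The plan reports A and D but not B, so the terms cannot be separated.

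**Reproducing the plan's figure.** The inputs from SAP 2.11 are annual rates r of 0.20 and 0.16, uniform accrual over 1.5 years and a 3-year study; SAP 1.1 gives 450 per arm. With exponential times, expected events per arm are 450 × [1 − (e^(−1.5r) − e^(−3r))/(1.5r)].
- r = 0.20: 450 × [1 − (0.7408 − 0.5488)/0.30] = 162.0
- r = 0.16: 450 × [1 − (0.7866 − 0.6188)/0.24] = 135.3

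The total is 297.3 against the stated 302, which is 1.6% lower. Simulated power was 0.775 to 0.87 over plausible values of the unstated NT-proBNP spread, consistent with 85%. The planning model is a fair base for an illustration.

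**Model 1: switching at a constant rate.** Assumptions not in the documents: log-SD of the NT-proBNP ratio 0.8, CV-death hazard doubled after HF hospitalisation, one stratum, no effect of the switch on outcome, and the non-CV death and switch rates shown. Switch rates are per year, sacubitril/valsartan then enalapril. A, B and D within a row use the same simulated data.

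| Scenario | A | B | D | B − A | D − B | D − A | Deaths dropped |
|---|---|---|---|---|---|---|---|
| Non-CV death 0.02/yr, neutral; no switching | 1.419 | 1.368 | 1.368 | −0.051 | 0 | −0.051 | 0 of 162 |
| Same; 0.02 and 0.02 | 1.412 | 1.369 | 1.374 | −0.043 | +0.005 | −0.038 | 4 of 162 |
| Same; 0.05 and 0.10, tripled after HF hospitalisation | 1.396 | 1.359 | 1.383 | −0.037 | +0.024 | −0.013 | 17 of 165 |
| Non-CV death 0.04/yr, HR 1.5; switching as in the row above | 1.432 | 1.238 | 1.275 | −0.194 | +0.037 | −0.157 | 19 of 208 |

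In the third row censoring masks 0.024/0.037 = 65% of the fall due to non-CV death; in the fourth, 0.037/0.194 = 19%.

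**Model 2: switching one month after a first HF hospitalisation.** SAP 2.11 puts 66% of first events as HF hospitalisation, so the enalapril rates are 0.66 × 0.20 = 0.132 and 0.34 × 0.20 = 0.068 for CV death, with HR 0.8. Assumptions: gamma frailty with variance 1 (rates × 1.2), CV-death hazard tripled after hospitalisation, non-CV death 0.02/yr in both arms, log-SD 0.7, no effect of the switch.

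| Hospitalised participants who switch | Enalapril deaths dropped (of about 105), enalapril-only switching | Death tier, enalapril-only | Overall, enalapril-only | Overall, equal switching |
|---|---|---|---|---|
| 20% | about 7 | 1.22 to 1.16 | 1.41 to 1.42 | 1.40 to 1.40 |
| 40% | about 14 | 1.22 to 1.12 | 1.38 to 1.41 | 1.40 to 1.40 |
| 60% | about 21 | 1.22 to 1.04 | 1.39 to 1.43 | 1.39 to 1.39 |

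Overall cells give B, then D. The level differs between rows because each is a fresh simulation. With equal switching the death tier hardly moves (about 1.21 to 1.19 at 60%). With enalapril-only switching the share of the non-CV fall that is offset is roughly 30% at the low end and 75% at the high end. Simulation noise is a few points: one 60% run gave A 1.433, B 1.390 and D 1.425, so 0.035/0.043 = 81%. Repeat runs at 60% put the death tier between 1.04 and 1.08.

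**The case against.** A supplementary estimand may differ from the primary in more than one attribute, and 2.5.1.2 does not claim to isolate non-CV death. The history entry about total death is filed under SAP 2.5.3, so it is weak evidence of the purpose of 2.5.1.2. That is fair, but 2.5.3 as it now stands holds no total-death analysis, so 2.5.1.2 is the only place where the hierarchical result can be seen with all deaths counted. The two changes stand in the current text whatever the log says.

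All-cause mortality is also a secondary endpoint, analysed by Cox model on the FAS (SAP 2.6.1, 2.6.2.1) with censoring rules that do not stop at a switch (2.6.2.5). Deaths after a switch are therefore not lost to the trial. This stands and limits the harm, but a hazard ratio does not show what happens to the win ratio. SAP 2.5.2.1 also counts undetermined deaths as CV deaths, which narrows what non-CV death could change.

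A reader might infer that the crossover rule is lopsided against one arm. The documents do not support that. Crossing to the other arm's drug is symmetric as a rule; only its frequency may differ, and no counts are given. What is fair to say is that the SAP does not define crossover or separate it from discontinuation followed by a permitted open-label drug. A reader might also infer that the overall win ratio would conceal a weakened mortality tier. SAP 2.5.2 reports wins by component, and 2.5.1.2 is to be conducted like the primary, so on that reading the tier would be visible.

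**Conclusion.** The point holds as one of estimand design. The plan changes the death definition and the crossover strategy together, so its one all-cause-death win ratio omits deaths after a switch and cannot show whether counting non-CV death alters the primary result. No stated figure is wrong.

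The numerical effect ranges from nil to modest. It vanishes without switching and is negligible when switching is equal in the two arms. The upper end of the range rests on switching in the enalapril arm alone, on switches that follow hospitalisation, and on the assumed hazard and non-CV death rates. Even there, a shift of 0.01 to 0.04 is small beside a 95% interval of about 1.18 to 1.66 around a win ratio of 1.40 (log SD about 0.0875: 1.40 × e^(±1.96 × 0.0875)). The shift matters mainly relative to the fall it masks. It would be wrong to infer any threat to the primary test, which is separate and carries the alpha.

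**What to change.** 1. Define the supplementary all-cause win ratio as all-cause death, then first HF hospitalisation, then Week 12 NT-proBNP, with treatment policy for both discontinuation and crossover. Only the death definition then differs from the primary.
2. Report the crossover-censored win ratio as a separate supplementary analysis with the primary CV-death hierarchy. Define crossover identically in both arms and distinctly from discontinuation, for example as the start of the other arm's study drug. A definition covering any open-label RAAS inhibitor would overlap with discontinuation, which Table 6 handles by treatment policy.
3. For that second analysis, say that censoring at the switch may be informative, and give per arm the number of switches and of later deaths and HF hospitalisations.
4. State the death definition used in each run, because Appendix 4.1 refers only to a patient who dies.

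This needs SAP wording and one more run of existing code, with no new data. The downside is one more supplementary table.
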